4.2. Study Schematic

4.3. Schedule of Assessments

Table 1. Screening Phase and DBT Phase Schedule of Assessments

	Screening Phase (3-28 days)	DBT Phase (up to 45 days in duration)				
Procedure	Screening Visit	Baseline/ Randomization (Day 1) ¹	Moderate or Severe Migraine Before Study Drug	Post Study Drug: Administration 15, 30, 45, 60, 90 minutes 2, 3, 4, 6, 8, 24 and 48 hours	End of Treatment – (DBT Phase) (7 days +2 days after dosing) ²	Notes
Eligibility Assessments						
Informed consent	X					Subject must be entered in the RTSM after informed consent is collected to obtain their study subject identification number.
Inclusion/ Exclusion criteria assessed	X	X				
Medical history	X					
Migraine history assessment (signs/ symptoms/ prior treatment/ frequency/ intensity)	X					
Concomitant medication paper diary	X	X		X	X	See Section 5.4 for additional details
Rescue Medication paper diary		X	X	X		

1 The **Baseline Visit** may only occur *after* all screening procedures are completed and the subject meets all inclusion/exclusion criteria. If the subject does not meet all eligibility requirements, the subject is to be counted as a Screen Failed within the RTSM system.

2 All subjects will return to the site (after assessments in the eDiary are completed) within 7 (+2) days after dosing with study drug in this phase. The “+2” day window is included for scheduling purposes only. Every effort should be made to conduct the DBT EOT Visit and maintain the 7 (+2) day window. However, due to concerns related to the COVID-19 pandemic, or any natural catastrophe, the DBT EOT Visit window may be modified beyond the 7 (+2) day window. Any potential issues should be discussed with Sponsor/CRO and will be addressed on an individualized basis.

	Screening Phase (3-28 days)	DBT Phase (up to 45 days in duration)				
Procedure	Screening Visit	Baseline/ Randomization (Day 1) ¹	Moderate or Severe Migraine Before Study Drug	Post Study Drug: Administration 15, 30, 45, 60, 90 minutes 2, 3, 4, 6, 8, 24 and 48 hours	End of Treatment – (DBT Phase) (7 days +2 days after dosing) ²	Notes
Randomize subject in RTSM		X				Obtain subject ID
Safety Assessments						

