6.3 Efficacy

Efficacy endpoints are assessed by as-randomized treatment group.

Randomization is stratified using the RTSM system, but analyses use the imputed randomization stratum, which is based primarily on the actual data (i.e., history of clinically relevant CV disease; see Section 6.2.5.1). The rationale for using the actual data in analyses is that sites may erroneously report the wrong stratum in the RTSM system. Hence, treatment group comparisons of binary efficacy endpoints are stratified by the imputed randomization stratum except within subgroups. If there are sparse data within a stratum, then results may be presented unstratified. Note that the phrase “randomization stratum” refers to the imputed randomization stratum throughout this section.

For binary efficacy endpoints, CIs are based on a normal approximation to the binomial distribution using asymptotic standard error (ASE). For continuous efficacy endpoints, CIs are based on the normal distribution. All CIs are 2-sided.

See Sections 7.2 and 7.3 for the definition of efficacy analysis periods and study days.

Efficacy Endpoints During the DBT Phase

During the DBT Phase, select endpoints are assessed over time at all scheduled time points postdose: 15, 30, 45, 60, and 90 minutes; 2, 3, 4, 6, 8, 24, and 48 hours.

Analyses are based on the DBT efficacy analysis set with eDiary measurement dates in the DBT Phase analysis period at planned time points of 15 minutes through 48 hours from the eDiary Migraine question category (see Section 7.4.2).

Efficacy Endpoints During the OLE Phase

Analyses are based on the OLE migraine analysis set with eDiary measurement dates in the OLE Phase analysis period from the eDiary Migraine question category (see Section 7.4.2).

Methods of Handling Missing Data

Methods of handling missing data in analyses of binary efficacy endpoints during the DBT Phase are defined as follows:

- Noncompleter = Failure (NC=F): Subjects with missing data at a single time point are classified as failures. This missing data imputation method is applied to endpoints based on data from a single time point (e.g., primary endpoint) as the main analysis method.

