7.1 Derived Dates

Derived dates are defined as follows:

- eDiary measurement date: derived for each record in the raw eDiary as follows:
 - eDiary reported study medication date if nonmissing, for any parameter in the Migraine question category at the time of study drug dosing (see Section 7.4.1.1)eDiary manual DCF study medication date, if nonmissing in the Manual DCF Study Medication question category (see Section 7.4.1.2)
 - eDiary finding date otherwise.
- DBT Phase start date: earlier of the RTSM randomization date or DB study drug date. This is an analysis period reference date.
- Study drug date/time: derived from either of the 2 following eDiary sources:
 - Reported: nonmissing eDiary reported study medication date/time (see Section 7.4.1.1)
 - Manual DCF: nonmissing eDiary manual DCF study medication date (see Section 7.4.1.2)

- Study drug start date/time: earliest study drug date/time. This is an analysis period reference date.
- Study drug end date: latest study drug date
- Study drug last date:
 - Before the final database lock: study drug end date derived only for subjects who have either (1) or (2):
 - (1) “yes” or “no” response to the question “Did the subject complete the DBT Phase?” from the DB Subject Status CRF, and “no” response to the question “Will the subject continue into the OLE Phase?” from the DB Subject Status CRF, and missing OL rimegepant start date
 - (2) “yes” or “no” response to the question “Did the subject complete the OLE Phase?” from the OLE Subject Status CRF
 - Final database lock: study drug end date

This is an analysis period reference date.

- First OL wallet dispensed date: earliest nonmissing wallet dispensed date with valid OL wallet ID from the Drug Accountability CRF (see Section 6.2.6.1)
- DB study drug date/time: earliest study drug date/time, if any of the following is met:
 - Earliest study drug date is before the first OL wallet dispensed date
 - Earliest study drug date is equal to the first OL wallet dispensed date, and $00:00 \leq$ earliest study drug time $< 07:00$. First OL wallet dispensed date is missing.

This is an analysis period reference date. DB study drug date/time can be either reported (time is not missing) or manual DCF (time is missing).

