- OL rimegepant date/time: study drug date/time (1) with study drug date on or after the first OL wallet dispensed date and (2) not classified as the DB study drug date/time. Note that although rare, it is possible for subjects to have multiple records on the same date. OL rimegepant date/time can be either reported (time is not missing) or manual DCF (time is missing).
- OL rimegepant start date/time: earliest OL rimegepant date/time. This is an analysis period reference date.
- OL rimegepant end date: latest OL rimegepant date. This is used to define OL rimegepant exposure.
- OL rimegepant last date:
 - Before the final database lock: OL rimegepant end date defined only for subjects with “yes” or “no” response to question “Did the subject complete the OLE Phase?” from the OLE Subject Status CRF.
 - Final database lock: OL rimegepant end date.

This is an analysis period reference date.

- DB or OL rimegepant start date/time: study drug start date/time for subjects whose as-treated DB treatment group is rimegepant; OL rimegepant start date/time for subjects whose as-treated DB treatment group is placebo. This is an analysis period reference date.
- DB or OL rimegepant end date: study drug end date for subjects whose as-treated DB treatment group is rimegepant; OL rimegepant end date for subjects whose as-treated DB treatment group is placebo
- DB or OL rimegepant last date: study drug last date for subjects whose as-treated DB treatment group is rimegepant; OL rimegepant last date for subjects whose as-treated DB treatment group is placebo. This is an analysis period reference date.
- OLE Phase start date: earlier of (1) DBT EOT visit date from the Visit Date CRF, or (2) OL rimegepant start date. This is an analysis period reference date.
- OLE Phase end date: latest of (1) OLE Phase start date, (2) OL rimegepant end date, or (3) latest complete visit date on or after the OLE Phase start date through the Week 12/EOT visit date (excluding the Follow-Up Week 2 visit date) from the Visit Date and Unscheduled Visit Checklist CRFs
- OLE Phase last date:
 - Before the final database lock: OLE Phase end date defined only for subjects with nonmissing study drug last date
 - Final database lock: OLE Phase end date.This is an analysis period reference date.

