7.2 Analysis Periods

Measurements are slotted into analysis periods based on comparing measurement dates to analysis period reference dates (time is not applicable).

Analysis periods are defined as follows:

- General
 - Screening Phase:
 - If the DBT Phase start date is nonmissing: measurement date before the DBT Phase start date
 - If the DBT Phase start date is missing: measurement date

This period is used to derive analysis visit windows for safety endpoints during the Screening Phase.
 - DBT Phase:
 - If the OLE Phase start date is nonmissing: measurement date on or after the DBT Phase start date through {OLE Phase start date – 1 day}
 - If the OLE Phase start date is missing: measurement date on or after the DBT Phase start date

This period is used to assess efficacy endpoints and outcomes research MQoL endpoints during the DBT Phase, and also to derive analysis visit windows for safety endpoints during the DBT Phase.
 - OLE Phase:
 - If the OLE Phase last date is nonmissing: measurement date on or after the OLE Phase start date through the OLE Phase last date
 - If the OLE Phase last date is missing: measurement date on or after the OLE Phase start date

This period is used to assess efficacy endpoints during the OLE Phase, and also to derive analysis visit windows for safety endpoints during the OLE Phase.

- Follow-up Phase: measurement date on or after the OLE Phase last date.
- Pretreatment characteristics and safety endpoints
 - Pretreatment:
 - If the study drug start date is nonmissing: measurement date/time on or before the study drug start date/time.
 - If the study drug start date is missing: measurement date/time.

This period is abbreviated as “PRETRT” in listings, and is used to derive baseline values. Note that AEs with imputed start date equal to the study drug start date are NOT part of this period.

- On-DBT safety:
 - If the OL rimegepant start date is nonmissing: measurement date/time after the DB study drug date/time through the earlier of DB study drug date + 9 days and OL rimegepant start date/time
 - If the OL rimegepant start date is missing: measurement date/time after the DB study drug date/time

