7.3 Analysis Visit Windows

Study days are calculated from the DBT Phase start date as follows:

- Measurement date – DBT Phase start date + 1, if measurement date \geq DBT Phase start date
- Measurement date – DBT Phase start date, if measurement date $<$ DBT Phase start date.

DBT days are calculated from the DB study drug start date as follows:

- Measurement date – DB study drug start date + 1, if measurement date \geq DB study drug start date
- Measurement date – DB study drug start date, if measurement date $<$ DB study drug start date.

OLE days are calculated from the OLE Phase start date as follows:

- Measurement date – OLE Phase start date + 1, if measurement date \geq OLE Phase start date
- Measurement date – OLE Phase start date, if measurement date $<$ OLE Phase start date.

OL rimegepant days are calculated from the OL rimegepant start date as follows:

- Measurement date – OL rimegepant start date + 1, if measurement date \geq OL rimegepant start date

- Measurement date – OL rimegepant start date, if measurement date < OL rimegepant start date.

Follow-up days are calculated from the OLE Phase last date as follows:

- Measurement date – OLE Phase last date + 1, if measurement date ≥ OLE Phase last date + 1
- Measurement date – OLE Phase last date, if measurement date < OLE Phase last date + 1.

General analysis visit windows (e.g. for safety parameters, MSQ, MIBS) are shown in Table 6.

Table 6 General Analysis Visit Windows

Analysis Period Analysis Visit	Abbreviation in Listings	Analysis Day Analysis Visit Window	Target Day
Screening Phase		Study Day	
Screening *		≤-1	
Baseline *		1	
Post-randomization @	Postrand	≥2	
DBT Phase		Study Day	
DBT EOT		≥2	
OLE Phase/OLE Outcomes Research		OLE Day	
Week 2		1 to 21	14
Week 4		22 to 42	28
Week 8		43 to 70	56
Week 12		71 to 98	84
Extension @	OLE Ext	≥99	
Follow-Up Phase			
Follow-Up Week 2	FU Week 2	1 to 21	14
Follow-Up Extension @	FU Ext	≥22	

* For subjects in the enrolled analysis set excluded from the full analysis set, the visit label is used for slotting.

@ Denotes an extended visit in the analysis period and is displayed only in listings

7.4 eDiary Data

The eDiary has the following question categories and key parameters which are used during the DBT and OLE Phases:

- Migraine question category:
 - Study medication parameters, from which the eDiary reported study medication date/time is derived (see Section 7.4.1.1)
 - Migraine characteristics parameters (see Section 7.4.2)

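### The DBT Phase ends by calendar date the day before the DBT EOT visit, so double-blind readings dated on that visit day are scored as failures and the DBT EOT analysis visit cannot contain the visit it is named after

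*SAP*

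**What the plan says.** SAP 7.2 sets the DBT Phase analysis period, when an OLE Phase start date exists, as "measurement date on or after the DBT Phase start date through {OLE Phase start date – 1 day". SAP 7.1 defines that start date: "OLE Phase start date: earlier of (1) DBT EOT visit date from the Visit Date CRF, or (2) OL rimegepant start date". The definition does not depend on whether the subject enters the OLE. SAP 7.2 compares dates only: "Measurements are slotted into analysis periods based on comparing measurement dates to analysis period reference dates (time is not applicable".

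Under SAP 7.1, parameters recorded at the time of dosing take the dose date. A postdose reading takes its "eDiary finding date otherwise". SAP 6.3 then restricts the efficacy data: "Analyses are based on the DBT efficacy analysis set with eDiary measurement dates in the DBT Phase analysis period at planned time points". Criterion 4 of the DBT efficacy set (SAP 4.1) applies the same period.

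On visit timing, Protocol Table 1, footnote 2, says: "All subjects will return to the site (after assessments in the eDiary are completed) within 7 (+2) days after dosing with study drug in this", meaning the double-blind part of the study. The synopsis, Protocol 4.1 and the Table 1 column header place the visit at about 7 days. SAP 2.1 gives 7 (± 2) days, while SAP 7.2 cites 7 (+2) days.

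On visit slotting, SAP 7.3 states: "General analysis visit windows (e.g. for safety parameters, MSQ, MIBS) are shown in Table 6". In Table 6 the DBT EOT visit covers study day 2 onward within the DBT Phase, and Week 2 covers OLE days 1 to 21.

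**The concern.** The calendar cut is applied to data that already have a better anchor. Table 7 ties each postdose reading to the reported double-blind dose time. The date filter can override this and discard a valid reading only because of the day on which the subject came to the clinic.

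A missing 48-hour reading is a failure for sustained return to normal function, sustained pain relief and sustained pain freedom from 2 to 48 hours (key secondary endpoints 5, 7 and 9). It also counts as a relapse in the pain relapse analysis and as a failure in the 48-hour time-point analyses. Endpoint 5 stands ahead of endpoints 6 to 10 in the fixed testing sequence, so false failures there also affect what may be tested later.

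The excluded reading does not vanish. Its date lies in the OLE Phase interval, and SAP 9.2.2 counts any date with a migraine pain intensity of mild or worse as an OLE migraine day. A double-blind outcome can therefore enter an OLE secondary endpoint.

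**Working it through.** **The plan's own figure.** With 57.9% vs 43.9% and 270 per arm (SAP 5), the pooled rate is 50.9%. The null standard error is √(2 × 0.509 × 0.491 / 270) = 0.0430, and the alternative standard error is √((0.579 × 0.421 + 0.439 × 0.561) / 270) = 0.0426. Power = Φ((0.140 − 1.96 × 0.0430) / 0.0426) = 0.904, which agrees with the stated 90%. The point does not depend on this figure.

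**Date of the 48-hour reading.** The Table 7 window runs from above 47 hours to below 49 hours 1 minute. A reading at exactly 48 hours falls on dose date +2. If dose and reading times are spread evenly (assumption), about 98% fall on +2 and about 1% each on +1 and +3.

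**Which visits lose it.** A reading is kept only if its date is no later than the visit date minus 1 day.

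| EOT visit | Reading dated +2 | Reading dated +3 |
|---|---|---|
| dose date +2 | lost | lost |
| dose date +3 | kept | lost |
| dose date +4 to +9 | kept | kept |

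For example, a subject doses on Monday at 08:00, completes the 48-hour entry on Wednesday at 08:00 and attends that afternoon. This is within the wording of Table 1, footnote 2, yet the Wednesday reading is dated on the OLE Phase start date and is dropped.

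**Dose on the EOT date.** SAP 7.1 classifies a dose before 07:00 on the first open-label wallet dispensed date as the double-blind dose. Protocol Table 2, footnote 4, has open-label wallets first given out at the DBT EOT visit. Every reading after such a dose is dated on or after the OLE Phase start date, so none can lie in the DBT Phase. The subject fails criterion 4 of SAP 4.1 and leaves the primary analysis. Sections 7.1 and 7.2 thus conflict for a case that the SAP itself anticipates.

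**Effect on a treatment difference.** Let f be the share of would-be responders whose 48-hour reading is dropped, equal in both arms. Each rate p becomes p(1 − f), so the difference is multiplied by (1 − f). The documents give neither f nor response rates for the 2 to 48-hour endpoints, so these are illustrations:
- A 10-point difference (40% vs 30%, assumed) becomes 10 × 0.99 = 9.9 points at f = 1% and 10 × 0.95 = 9.5 points at f = 5%.
- With the primary-endpoint rates as placeholders, 14.0 points becomes 13.9 at 1% and 13.3 at 5%. Power by the formula above goes from 90.4% to 89.9% and 87.3%.

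**Visit slotting.** If the EOT visit date is the OLE Phase start date, its OLE day is (visit date − visit date) + 1 = 1, which Table 6 assigns to Week 2. The DBT EOT window lies inside a period that closed the day before, so it cannot hold the visit's measurements.

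**The case against.** The best defence is that the efficacy trigger is off-schedule. Most statements of the visit put it at about day 7, SAP 2.1 would put it on days 5 to 9, and Protocol 5.5.2.1 describes an interval between the 48-hour assessments and the visit. Visits on +4 to +9 lose nothing. This stands, and it limits how often the rule can bite. It does not make the rule correct, because the footnote sets no earliest day beyond completion of the eDiary assessments. The dose on the EOT date is likewise an edge case, and nothing suggests that it is common.

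The boundary also follows the protocol, which makes the DBT EOT visit OLE Day 1, and assigning that date to one phase avoids double counting. That is a sound reason for OLE diary-day counts. It is no reason to discard readings tied to the double-blind dose.

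A reader might infer that DBT EOT safety data are misreported in the by-arm tables. The documents do not support that. SAP 6.4 assigns safety periods in a separate step, and the on-DBT safety period runs to the earlier of dose date + 9 days and the first open-label dose. The change tables report EOT within that period, with a derivation left to the Core SAP, which is not available here. On-OL summaries need measurements after the first open-label dose. SAP 6.1.1.3 also prints the analysis period and DBT day beside the visit label in safety listings.

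**Conclusion.** The point holds as a rule that gives wrong results in defined cases, not as evidence of widespread data loss. The 48-hour reading is at risk only with a visit on about dose date +2 or +3. The primary analysis is touched in ordinary conduct only when the double-blind dose falls on the EOT date. The Week 2 label applies to measurements at the DBT EOT visit generally, including for subjects who never enter the OLE, but it matters mainly in listings.

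A reader might infer a loss of up to about 2 percentage points (5% affected × 40% responding = 2.0). That would be the fall in one arm's rate, not in the tested difference, and both inputs are assumptions. The cut ignores treatment. With equal f the difference shrinks towards zero by the factor (1 − f), which is 0.1 to 0.5 points on an illustrative 10 at f = 1% to 5%. The equality of f, and its independence from response within each arm, are assumptions.

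**What to change.** 1. For DBT efficacy and DBT MQoL, replace the calendar-date filter in SAP 4.1 (criterion 4), 6.3, 6.5.1 and 7.2. Use readings that fall in a Table 7 window relative to the reported double-blind dose date/time and that precede the first open-label rimegepant dose.
2. State that those readings do not count as OLE migraine-day data (SAP 9.2.2).
3. For visit-based parameters, slot measurements dated on the DBT EOT visit and before the first open-label dose to DBT EOT, and start the OLE Week 2 window after that date.
4. Reconcile the visit-window statements: 7 (+2) days in the protocol and SAP 7.2, and 7 (± 2) days in SAP 2.1.

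No new data are needed. The cost is a small amount of derivation wording and programming, with separate boundaries for eDiary and visit data. Because the change affects membership of the DBT efficacy set, it belongs in the SAP rather than only in dataset specifications, and it should be settled while the study is blinded, that is, before the PCD database lock.

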- Interim safety: subjects in the OL rimegepant safety analysis set with OL rimegepant start date – DB study drug date > 9 days. This analysis set is used to assess post-DBT pre-OL rimegepant safety.
- Follow-up safety: subjects in the safety analysis set whose last contact date is in the follow-up safety analysis period. This analysis set is used to assess follow-up safety.
- DB or OL rimegepant safety: subjects in the safety analysis set who take ≥ 1 dose of DB or OL rimegepant, i.e., nonmissing DB or OL rimegepant start date. This analysis set is used only to produce safety narrative subject identifiers.

See Section 7.1 for derived dates and 7.2 for analysis periods.

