This period is abbreviated as “DBT” in safety listings, and is used to assess safety endpoints on DBT for the DBT safety analysis set. The 9-day cut reflects the protocol-defined visit window of 7 (+2) days after DB study drug dosing for the DBT EOT Visit. Note that AEs with imputed start date equal to the DB study drug date are part of this period, and AEs with imputed start date equal to the OL rimegepant start date are NOT part of this period.

- Post-DBT pre-OL rimegepant safety: measurement date after the DB study drug date + 9 days through the OL rimegepant start date/time.

This period is abbreviated as “INT” in safety listings, and is used to assess safety endpoints during the interim period (i.e., post-DBT pre-OL rimegepant) for the interim safety analysis set (i.e., those with >9-day gap between DB study drug date and OL rimegepant start date). Note that AEs with imputed start date equal to the OL rimegepant start date are NOT part of this period.

- On-OL rimegepant safety:
 - If the OL rimegepant last date is nonmissing: measurement date/time after the OL rimegepant start date/time through the OL rimegepant last date + 9 days
 - If the OL rimegepant last date is missing: measurement date/time after the OL rimegepant start date/time

This period is abbreviated as “OLRMG” in safety listings, and is used to assess safety endpoints on OL rimegepant for the OL rimegepant safety analysis set. Note that AEs with imputed start date equal to the OL rimegepant start date are part of this period.

- On-DB or OL rimegepant safety:
 - If the DB or OL rimegepant last date is not missing: measurement date/time after the DB or OL rimegepant start date/time through the DB or OL rimegepant last date + 9 days
 - If the DB or OL rimegepant last date is missing: measurement date/time after the DB or OL rimegepant start date/time

This period is used to assess safety endpoints on DB or OL rimegepant for the DB or OL rimegepant safety analysis set. Note that AEs with imputed start date equal to the DB or OL rimegepant start date are part of this period.
- Follow-up safety: measurement date after the study drug last date + 9 days. This period is abbreviated as “FU” in safety listings, and is used to assess safety endpoints during follow-up for the follow-up safety analysis set.
- OLE outcomes research: assessment date/eDiary measurement date on or after the OLE Phase start date. This period is used to assess outcomes research MQoL, MSQ, and MIBS endpoints.

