7.6 Nonstudy Medication Types

See Section 7.1 for derived dates.

DBT Concomitant Medications

DBT concomitant medications are defined as nonstudy medications taken within 9 days after DB study drug dosing and before the first dose of OL rimegepant, i.e., those meeting any of the following criteria:

- DB study drug date ≤ imputed start or imputed end date ≤ minimum{DB study drug date + 9 days; OL rimegepant start date – 1 day}
- DB study drug date ≤ imputed start or imputed end date ≤ DB study drug date + 9 days, if OL rimegepant start date is missing
- Imputed start date ≤ DB study drug date ≤ minimum{DB study drug date + 9 days; OL rimegepant start date – 1 day} ≤ imputed end date
- Imputed start date ≤ DB study drug date ≤ DB study drug date + 9 days ≤ imputed end date, if OL rimegepant start date is missing.

The 9-day window is chosen to align with the on-DBT safety analysis period (see Section 7.2).

Post-DBT Pre-OL Rimegepant Medications

Post-DBT pre-OL rimegepant medications are defined as nonstudy medications taken after DB study drug dosing + 9 days and before the first dose of OL rimegepant, i.e., those meeting any of the following criteria:

- DB study drug date + 9 days < imputed start or imputed end date < OL rimegepant start date
- Imputed start date < DB study drug date + 9 days < OL rimegepant start date < imputed end date.

OL Rimegepant Concomitant Medications

OL rimegepant concomitant medications are defined as nonstudy medications taken from the first dose of OL rimegepant through the last dose of OL rimegepant + 9 days, i.e., those meeting any of the following criteria:

- OL rimegepant start date ≤ imputed start or imputed end date ≤ OL rimegepant last date + 9 days
- OL rimegepant start date ≤ imputed start or imputed end date, and OL rimegepant last date is missing
- Imputed start date ≤ OL rimegepant start date ≤ OL rimegepant last date + 9 days ≤ imputed end date
- Imputed start date ≤ OL rimegepant start date ≤ imputed end date, and OL rimegepant last date is missing.

The 9-day window is chosen to align with the on-OL rimegepant safety analysis period (see Section 7.2).

Follow-Up Medications

Follow-up medications are defined as nonstudy medications taken after study drug discontinuation + 9 days, i.e., study drug last date + 9 days < imputed start date or imputed end date.

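### The on-DBT safety period has no end when open-label rimegepant is never started, so later events in those subjects meet both the on-DBT and the follow-up definitions

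*SAP*

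**What the plan says.** SAP section 7.2 defines on-DBT safety in two branches. If OL rimegepant was started, the period covers "measurement date/time after the DB study drug date/time through the earlier of DB study drug date + 9 days and OL rimegepant start date/time". If it was not, the rule is "If the OL rimegepant start date is missing: measurement date/time after the DB study drug date/time" and stops there. A note below gives the reason for the limit: "The 9-day cut reflects the protocol-defined visit window of 7 (+2) days after DB study drug dosing for the DBT EOT Visit".

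The same section defines the last period as "Follow-up safety: measurement date after the study drug last date + 9 days". Section 7.1 has "Study drug end date: latest study drug date", and at the final lock the study drug last date is set equal to that end date. Section 4.1 builds the follow-up safety set from "subjects in the safety analysis set whose last contact date is in the follow-up safety analysis period"; an OL dose is not required.

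Section 7.6 caps DBT concomitant medications at the DB dose date + 9 days when the OL start date is missing, and explains: "The 9-day window is chosen to align with the on-DBT safety analysis period".

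**The concern.** DB treatment is one tablet, so its on-treatment period can be closed from the dose date alone. A missing OL start date does not mean that DB treatment is continuing. Under the second branch, an adverse event or laboratory value found weeks later is tabulated as on-DBT, and at the final lock it also qualifies as follow-up. No rule says which period takes precedence. Section 6.1.1.3 nevertheless lists a single period for each measurement, which presupposes that the periods do not overlap.

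The tables at stake are the on-DBT summaries of AEs, SAEs and grade 3 to 4 laboratory abnormalities (other secondary objective 4), LFT elevations (exploratory objective 16), ECG abnormalities and C-SSRS. A subject who enters the OLE but takes no OL drug still has LFTs at Week 4 and laboratory tests, ECG and C-SSRS at Week 12 (protocol Table 2). As written, all of these fall in the on-DBT period.

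**Working it through.** Days are counted from the DB dose (day 0).

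**1. The plan's own figure.** The DBT EOT Visit is due at 7 (+2) days (protocol section 4.3.2.2): 7 + 2 = 9 days. This reproduces the SAP's cut. Every dosed subject has that visit window, so the reason does not depend on OL start.

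**2. The two rules side by side.**

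| Rule | OL start recorded | OL start missing |
|---|---|---|
| On-DBT safety (SAP 7.2) | ends at the earlier of day 9 and OL start | no end |
| DBT concomitant medication (SAP 7.6) | ends at the earlier of day 9 and the day before OL start | ends at day 9 |

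The second rule is said to align with the first. When OL start is missing, it does not.

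**3. Where follow-up begins for a DB-only subject at the final lock.** Latest study drug date = DB dose date, so study drug last date = day 0. Follow-up safety is then any day > 0 + 9.

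**4. Slotting events in a DB-only subject at the final lock.**

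| Event day | As written | With a cap at day 9 |
|---|---|---|
| 5 | on-DBT | on-DBT |
| 9 | on-DBT | on-DBT |
| 10 | on-DBT and follow-up | follow-up |
| 21 | on-DBT and follow-up | follow-up |
| 60 | on-DBT and follow-up | follow-up |
| 105 | on-DBT and follow-up | follow-up |

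**5. How long the open window can run.** OLE Day 1 is the DBT EOT Visit, Week 12 is OLE Day 85 (+2), and the Follow-up Week 2 Visit is 14 (±2) days later.
- Nominal: 7 + 84 + 14 = 105 days.
- With all visit windows used: 9 + (84 + 2) + (14 + 2) = 111 days.

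**6. Who is affected.**
- *Dosed, does not enter the OLE.* The last scheduled visit is at day 7 (+2). Protocol section 4.3.4 requires the Follow-up Week 2 Visit only of OLE entrants. Data after day 9 come only from delayed or unscheduled visits and late reports.
- *Enters the OLE, never takes OL drug.* The window is the full 105 days or so. The documents give no count.
- *In the OLE, undosed at the PCD lock.* The window is open at that lock. If OL drug starts later, the same events are classed differently at the LSLV lock.

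**7. Would the cap alone be enough?** Take an event on day 20 in an OLE subject not yet dosed at the PCD lock, treating that lock as before the final one.
- As written, it is on-DBT. If OL drug starts after day 20, it becomes an interim event at the LSLV lock.
- With the cap alone, it is outside on-DBT. The interim set (section 4.1) needs an OL start date. Study drug last date is not derived for this subject (section 7.1), so follow-up is undefined. The event would be in no period table of the PCD report, only in listings.

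The repair therefore needs a second part.

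**The case against.** The strongest defence is that the SAP also leaves the on-OL and OLE Phase periods open when their closing date is missing. In those cases, however, treatment or the phase is still running, and the date is filled by the final lock. The on-DBT end never depends on a date yet to come, and for a subject who never takes OL drug the gap is never filled.

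A second defence is that the follow-up columns in SAP Table 5 are labelled only for subjects going on to OL rimegepant, so follow-up may have been meant for them alone. The definition of the follow-up set does not say so.

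Third, section 7 lets dataset specifications modify its conventions, and counting rules sit in a Core SAP that is not available here. The programmed tables may already handle this. That limits certainty about the output, but does not reconcile sections 7.2 and 7.6.

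Several stronger readings are tempting but not supported:
- *About 30 subjects, or 5.6%, carry weeks of extra on-DBT time* (540 − 510 = 30; 30/540 = 5.6%). These are two rounded planning estimates, and the subjects they describe do not enter the OLE, so their scheduled observation ends by about day 9. The figure does not measure the problem.
- *The arms are compared with bias.* The protocol presents safety descriptively, with no test. OLE entry does not require response, and both arms are offered the same drug. The documents give no reason to expect OL start to differ by arm.
- *Totals are inflated.* The overlap puts one event in two separately titled period tables. No table that adds them was identified.
- *The plus-9-days while-on-treatment rule in SAP section 3.2 is contradicted.* That text concerns discontinuation during the OLE Phase, so it is not direct evidence about the DB dose.

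**Conclusion.** The rule is wrong as written, and the error is narrow. The open-ended branch conflicts with the stated basis for the 9 days and with section 7.6. At the final lock it makes every event after day 9 in a DB-only subject both on-DBT and follow-up.

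The material case is the OLE entrant who never takes OL drug: about 105 days in place of 9. How many such subjects there will be cannot be derived from the documents. Enrolment requires 4 to 14 migraine days per month and the OLE lasts 12 weeks, so the number is probably small. A single misplaced SAE or grade 3 to 4 result would still be visible in the tables for a one-tablet phase.

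The effect is confined to descriptive safety tables. Efficacy and power are untouched. The conclusion assumes that no unseen specification already closes the window and, for the PCD point, that the PCD lock counts as before the final lock.

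**What to change.** 1. In SAP section 7.2, end the second on-DBT branch at DB study drug date + 9 days, as section 7.6 already does.
2. For subjects with a missing OL start date and no derived study drug last date (in the OLE but undosed at the PCD lock), assign measurements after day 9 to the post-DBT pre-OL rimegepant period through the data cut. Extend the interim safety set in section 4.1 to include them.
3. State that all other measurements after day 9 in DB-only subjects belong to follow-up safety only.

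The cost is a few sentences in sections 4.1 and 7.2 and the matching programming; no new data are needed. There is one small loss: DBT EOT laboratory and ECG values taken after day 9 in DB-only subjects leave the on-DBT tables. Protocol Table 1 allows such late visits in some circumstances, and it requires the DBT EOT ECG only of subjects not eligible for the OLE, so some of these ECGs could be affected. Late EOT values in OL starters are already excluded in the same way, so the change treats both groups alike.
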